5.3 Screen Failures

Screen failures are defined as patients who consent to participate in the clinical study but who do not meet 1 or more criterion required for participation and are not subsequently

entered in the study. A minimal set of screen failure information is required to ensure transparent reporting of screen failure patients, to meet the Consolidated Standards of Reporting Trials publishing requirements, and to respond to queries from regulatory authorities. Minimal information includes demography, screen failure details, eligibility criteria, and any SAE.

5.3.1 *Retesting During Screening*

Laboratory parameters and/or assessments that are included in the screening procedures ([Table 1](#)) may be repeated during the Screening Period in consultation with the sponsor's medical monitor. Retesting will be allowed when the significance of a laboratory result is unclear and the retest will help interpretation and decision making for entry to the study. Retesting will not be undertaken when the laboratory results clearly indicate clinically significant disease that could impact study interpretation or the safety of a study subject during participation.

The most current result prior to randomization is the value by which study inclusion will be assessed, as it represents the participant's most current clinical state.

5.3.2 *Rescreening*

This study will permit 1 rescreening of a participant who has failed 1 or more inclusion or exclusion criteria. Consultation with the medical monitor may be needed to identify whether rescreening is clinically relevant. If rescreened, the participant must sign a new ICF and the same Patient Number will be assigned.

For participants who are rescreened, consult with the medical monitor to confirm which parameters and/or assessments that were collected as part of the original Screening Period procedures may be utilized.

5.4 Premature Discontinuation

5.4.1 *Premature Discontinuation of Study Medication*

Patients should be permanently discontinued from study medication in the event of any of the following:

- The patient experiences significant worsening of AD such that additional therapy for the treatment of AD is required
- Confirmed, active infection with the SARS-CoV-2 virus
- Infection requiring parenteral antimicrobial therapy or hospitalization
- Symptomatic herpes zoster
- Malignancy – except for nonmelanoma skin cancer not in or near the treatment area
- Anaphylactic or severe allergic reaction
- WBC count: $<1 \times 10^9/L$ or second occurrence of $<2 \times 10^9/L$ – in each case, value should be confirmed by retesting before treatment discontinuation

- ANC: $<0.5 \times 10^9/L$ or second occurrence of $<1 \times 10^9/L$ – in each case, value should be confirmed by retesting before treatment discontinuation
- Lymphocyte count: $<0.3 \times 10^9/L$ or second occurrence of $<0.5 \times 10^9/L$ – in each case, value should be confirmed by retesting before treatment discontinuation
- Platelet count: $<50 \times 10^9/L$ or second occurrence of $<75 \times 10^9/L$ – in each case, value should be confirmed by retesting before treatment discontinuation
- Hemoglobin: $<6.5 \text{ g/dL}$ or second occurrence of $<8 \text{ g/dL}$ – in each case, value should be confirmed by retesting before treatment discontinuation
- AST or ALT:
 - $5 \times \text{ULN}$ persisting for 2 weeks of study medication interruption or second event of $>5 \times \text{ULN}$
 - $>3 \times \text{ULN}$ and (total bilirubin $>2 \times \text{ULN}$ or international normalized ratio [INR] of >1.5)
 - $3 \times \text{ULN}$ with total bilirubin $>2 \times \text{ULN}$ or symptoms of hepatocellular injury [fatigue, nausea, vomiting, right upper quadrant pain or tenderness, fever, rash and/or eosinophilia ($>5\%$)].
- Any patient who develops any of the following ECG findings during the active treatment phase will be instructed to stop study medication and will be withdrawn from the study:
 - Clinically significant rhythm disturbance other than sinus rhythm or ectopic supraventricular rhythm (ectopic atrial rhythm).
 - Clinically significant conduction disturbance including PR $>240 \text{ msec}$, pre-excitation (delta wave and PR $<120 \text{ msec}$), second degree or higher atrioventricular block.
 - New finding of QRS $>120 \text{ ms}$ (if not present at the Screening Visit. For example, patients with Right Bundle Branch Block at screening would not need to be withdrawn from the study if their subsequent ECGs remained unchanged).
 - Evidence of QT-interval prolongation, defined as an increase in the QTcF interval $>60 \text{ ms}$ from Visit 1.
 - Acute signs of ischemia or infarction.
 - Any ECG abnormality that may, in the opinion of the investigator, represent a new medical issue of concern.

In addition, patients should discontinue study medication if any of the following occurs:

1. The patient withdraws his/her consent to participate in the study.
2. The patient develops an illness that would interfere with his/her continued participation in the study.
3. The patient is noncompliant with study procedures or medication, in the opinion of the investigator.
4. The patient is confirmed to be pregnant.
5. The sponsor or regulatory agency requests withdrawal of the patient.

If a patient is prematurely discontinued from study medication, the patient may remain in the study. The patient should complete the assessments outlined for each study visit; see [Table 1](#). The patient should also attend the PTFU Visit.

Every effort will be made to ensure that patients who prematurely discontinue study medication complete the study.

Patients who discontinue study medication prematurely will not be replaced.

Patients are permitted to temporarily discontinue and restart study medication.

5.4.2 *Premature Discontinuation from the Study*

Participation in the study is strictly voluntary. A patient has the right to withdraw from the study at any time for any reason, without any reprisal.

At the time of premature study discontinuation, the investigator should make every effort to ensure the patient completes the assessments indicated at the Day 28/ET Visit and completes the PTFU Visit approximately 14 days after the ET Visit; see Table 1. The only exception to this requirement is when consent is withdrawn for all study procedures or the participant loses the ability to consent freely (e.g., is imprisoned or involuntarily incarcerated for the treatment of either a psychiatric or physical illness).

If a patient withdraws consent to participate in the study, the study monitor/sponsor will be informed immediately. If there is a medical reason for withdrawal, the patient should remain under the supervision of the investigator until satisfactory health has returned.

If the patient withdraws consent for disclosure of further information, the sponsor may retain and continue to use any collected data before such a withdrawal of consent. If a patient withdraws from the study, he/she may request destruction of any samples taken and not tested, and the investigator must document this in the site study records.

Although a patient is not obliged to give his/her reason(s) for withdrawing prematurely from a study, the investigator should make a reasonable effort to ascertain the reason(s), while fully respecting the patient's rights.

Patients who prematurely discontinue from the study cannot subsequently rejoin the study.

For details on the discontinuation of study sites or the study as a whole, see [Section 15](#).

5.4.3 *Lost to Follow-up*

A patient will be considered lost to follow-up if he/she repeatedly fails to return for scheduled visits and is unable to be contacted by the study site.

The following actions must be taken if a patient fails to return to the clinic for a required study visit:

- The site must attempt to contact the patient and reschedule the missed visit as soon as possible, counsel the patient on the importance of maintaining the assigned visit schedule, and ascertain whether or not the patient wishes to and/or should continue in the study.
- Before a patient is deemed lost to follow-up, the investigator (or designee) must make every effort to regain contact with the patient (where possible, 2 telephone calls and a certified letter to the patient's last known mailing address or local equivalent methods). These contact attempts should be documented in the patient's source record.

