6.3 Safety Assessments

6.3.1 *Adverse Events*

AEs will be followed, recorded, and reported in line with the procedures described in [Section 8](#).

6.3.2 *Clinical Laboratory Evaluations*

All laboratory samples will be processed and shipped to the central laboratory, as described in the Laboratory Manual. The central laboratory will analyze the samples or send them to reference laboratory(ies) for analysis, as indicated in the manual. Refer to the central Laboratory Manual for the maximum total volume of blood to be collected per patient throughout the study.

Non-fasting blood and urine samples will be collected at the times indicated in Table 1. On dosing day(s) sampling for the analysis of clinical laboratory parameters will be performed before the administration of study medication.

The following parameters will be assessed:

Hematology: hemoglobin, hematocrit, red blood cell (RBC) count, RBC morphology, platelets, total WBC count, differential WBC count, lymphocyte count, and ANC

Biochemistry: albumin, alkaline phosphatase, ALT, amylase, AST, blood urea nitrogen, bicarbonate, calcium, chloride, creatine phosphokinase (CPK), creatinine, phosphorus, gamma glutamyltransferase (GGT), glucose, lactate dehydrogenase (LDH), lipase, LDL-C, HDL-C, potassium, sodium, total and direct bilirubin, TC, and triglycerides (TG)

Urinalysis: pH, specific gravity, creatinine, glucose, bilirubin, blood, and protein

Screening serology tests will be performed to assess HIV (antibody), hepatitis C (antibody), hepatitis B surface antigen, or hepatitis B core antigen antibody. For hepatitis B, the following tests will be done at the Screening Visit and patients with a positive result for either hepatitis B surface antigen and or hepatitis B core antigen antibody will be excluded from the study.

Serum (β -human chorionic gonadotrophin) pregnancy testing will be performed at the Screening Visit, and urine pregnancy tests will be performed at the other study visits in the Treatment Period.

Refer to the Laboratory Manual for details regarding the collection, processing, and shipping of the blood and urine samples.

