6.3.2.1 Potential Drug-induced Liver Injury

Hy's Law cases have the following 3 components:

1. The drug causes hepatocellular injury, generally shown by a higher incidence of ≥ 3 -fold elevations above the ULN of ALT or AST than the placebo
2. Among study patients showing such aminotransferase elevations, often with aminotransferases much greater than $3 \times \text{ULN}$, one or more also shows elevation of serum total bilirubin to $> 2 \times \text{ULN}$ or INR > 1.5 , without initial findings of cholestasis (elevated ALP)
3. No other reason can be found to explain the combination of increased aminotransferase and total bilirubin, such as viral hepatitis A, B, or C; evidence for biliary obstruction; acute alcoholic hepatitis (recent drinking and AST $> 2 \times \text{ALT}$ are supportive); recent history of severe hypotension or congestive heart failure; other underlying viral disease; pre-existing or acute liver disease; or another drug (including non-prescription products such as herbal supplements) capable of causing the observed injury

During the study, the investigator will remain vigilant for increases in liver biochemistry. The investigator is responsible for determining whether a patient meets potential drug-induced liver injury criteria at any point during the study.

In the event that a patient shows laboratory results of:

- AST or ALT: $> 5 \times \text{ULN}$ persisting for 2 weeks after study medication interruption or second occurrence of $> 5 \times \text{ULN}$
- $\geq 3 \times \text{ULN}$ and (total bilirubin $\geq 2 \times \text{ULN}$ or INR > 1.5)
- $\geq 3 \times \text{ULN}$ with appearance of fatigue, nausea, vomiting, right upper quadrant pain or tenderness, fever, rash and/or eosinophilia ($> 5\%$)

Please refer to [Appendix 4](#) for further information.

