7.4.2 Dose Modification

Study medication dosing for individual patients will be allowed to be paused and restarted if it is deemed to be in the best interest of the patient's safety due to AE. Decisions regarding dose interruptions or modifications will be made by the investigator in consultation with the medical monitor based on the clinical evaluation of the patient. All treatment interruptions and the reason for the interruption should be recorded in the eCRF.

Treatment with ATI-1777 should be temporarily interrupted in the event of severe AEs considered related to ATI-1777, or in the event of one or more of the abnormal laboratory values in Table 5.

Table 5 Study Medication Interruption Criteria

Laboratory Test	Hold Study Medication if:	Resume Study Medication if:
WBC count	$<2 \times 10^9/L$	$\geq 2.5 \times 10^9/L$
ANC	$<1 \times 10^9/L$	$\geq 1.5 \times 10^9/L$
Lymphocyte count	$<0.5 \times 10^9/L$	$\geq 0.75 \times 10^9/L$
Platelet count	$<75 \times 10^9/L$	$\geq 100 \times 10^9/L$
Hemoglobin	8 g/dL or a decrease >2 g/dL	≥ 10 g/dL
AST or ALT	$>3 \times ULN$	$<2 \times ULN$ or within 20% of baseline values
Serum creatinine	$>2 \times ULN$	$<1.5 \times ULN$ or within 10% of baseline value

ALT = alanine aminotransferase; ANC = absolute neutrophil count; AST = aspartate aminotransferase; ULN = upper limit of normal range; WBC = white blood cell

If a patient has one or more of the abnormal laboratory values noted in [Table 5](#), the investigator or designee upon receipt and review of the central laboratory report should instruct the patient to hold study medication applications. The investigator or designee should ask the patient about symptoms, concomitant illnesses and medications and repeat the test(s) as soon as possible. The medical monitor must be notified of dose interruptions due to AEs or laboratory abnormalities noted in Table 5.

If the retest confirms the abnormal laboratory value, then the study medication should continue to be held followed by repeat testing once a week or sooner at the discretion of the investigator. The patient should be followed until the laboratory abnormality(s) returns to normal or to baseline values.

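### The Table 5 hold-and-restart path orders no INR, so an isolated AST or ALT rise can be held and restarted with the INR limb of the permanent-discontinuation rule untested (minor)

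*Protocol*

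**What the plan says.** **Where INR decides something.** Protocol 5.4.1 lists AST or ALT above 3 × ULN with bilirubin above 2 × ULN, or with an "international normalized ratio [INR] of >1.5", as a reason to stop study medication permanently. Section 6.3.2.1 uses nearly the same pair (≥3 × ULN with bilirubin ≥2 × ULN or INR >1.5) as the second of three criteria introduced by "In the event that a patient shows laboratory results of", and then refers to Appendix 4. It also puts INR >1.5 in its description of Hy's law, which is an individual stopping rule in 4.4.1.

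**What is measured.** Table 1 schedules chemistry, hematology and urinalysis. In 6.3.2 the hematology list reads "Hematology: hemoglobin, hematocrit, red blood cell (RBC) count, RBC morphology, platelets, total WBC count, differential WBC count, lymphocyte count, and ANC". The biochemistry list includes ALT, AST and bilirubin. INR is in none of the lists.

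**What happens when AST or ALT rises.** Under 7.4.2 and Table 5, drug is held above 3 × ULN, the patient is asked about symptoms, and the site is to "repeat the test(s) as soon as possible". If the rise is confirmed, the hold continues with "repeat testing once a week or sooner at the discretion of the investigator". Drug may resume below 2 × ULN or within 20% of baseline.

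**Where INR is ordered.** Only in Appendix 4, as a follow-up assessment to be rechecked with each set of liver chemistry.

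**The concern.** A permanent-discontinuation rule protects patients only if the measurement it depends on is taken when the rule could apply. Here the protocol defines its own path for an AST or ALT above 3 × ULN, from hold through retest to restart, and that path can be completed without an INR. A patient who in fact met the permanent rule could be put back on drug because nobody looked.

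For ALT rises there is a second consequence. Appendix 4, footnote 2 requires ALT ≥3 × ULN with INR >1.5 to be reported as an SAE, and such a case could go unrecognised. This is a first-in-human study in which liver enzyme elevation is an adverse event of special interest (8.1.5).

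**Working it through.** This is mainly a cross-reading; the plan states no figure to reproduce.

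**Step 1. Can each 6.3.2.1 criterion be judged from tests already ordered?**

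| Route to Appendix 4 | Data needed | Ordered before Appendix 4? |
|---|---|---|
| >5 × ULN, persistent after 2 weeks' interruption or recurrent | AST, ALT | Yes (6.3.2 panel, 7.4.2 retest) |
| ≥3 × ULN with bilirubin ≥2 × ULN | AST, ALT, bilirubin | Yes (6.3.2 panel) |
| ≥3 × ULN with INR >1.5 | AST, ALT, INR | **No INR** |
| ≥3 × ULN with listed symptoms or eosinophilia >5% | AST, ALT, symptoms, differential count | Yes (6.3.2 panel, 7.4.2 symptom enquiry) |

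INR is one of two alternatives in one of three criteria. A patient who meets any of the other routes reaches Appendix 4 and gets an INR there.

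**Step 2. Follow the patient who meets none of the others.** Take AST or ALT above 3 × ULN, bilirubin below 2 × ULN, no listed symptom, no eosinophilia above 5%, and no persistent or recurrent value above 5 × ULN.

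- Every route in the table is negative except INR, which is unknown.
- Appendix 4 is therefore not triggered unless INR is already known to exceed 1.5, yet Appendix 4 is the only place that orders INR. For this patient the reference is circular.
- Table 5 applies: drug is held and AST/ALT repeated. Once the value is below 2 × ULN or within 20% of baseline, drug may resume. No step asks for an INR or points to Appendix 4.

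**Step 3. Does Appendix 4 catch this patient some other way?** It has a monitoring branch for ALT ≥3 × ULN with bilirubin <2 × ULN and INR ≤1.5, with follow-up assessments within 24 to 72 hours. That branch presupposes an INR result and names ALT only, whereas 5.4.1, 6.3.2.1 and Table 5 use AST or ALT. An AST-only rise matches neither monitoring branch.

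**Step 4. How many patients might enter this path?** The documents give no incidence. For an assumed per-patient rate *p* of such an isolated rise, the chance of at least one among *n* patients is 1 − (1 − *p*)^*n*. About 50 patients are randomized 1:1, so about 25 receive ATI-1777.

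| Assumed *p* | *n* = 25 (active) | *n* = 50 (all) |
|---|---|---|
| 0.5% | 12% | 22% |
| 1% | 22% | 39% |
| 2% | 40% | 64% |
| 5% | 72% | 92% |

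For example, 1 − 0.99^25 = 0.222. The expected number entering the path is *np*, from 25 × 0.005 = 0.125 to 50 × 0.05 = 2.5 patients. Harm would also require an INR above 1.5 and a decision to restart, so these figures overstate the chance of an actual missed stop.

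**The case against.** The best case for the plan is that INR is clearly expected. Appendix 4 orders it, its low-bilirubin branch describes an isolated ALT rise, and the synopsis names coagulation among the laboratory data to be processed. Section 6.3.2.1 adds: "The investigator is responsible for determining whether a patient meets potential drug-induced liver injury criteria at any point during the study". An investigator cannot fully discharge that duty without an INR. Laboratory tests may be done at unscheduled visits (4.2), and the Laboratory Manual, which is not available here, might contain a reflex instruction.

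Nor is restart automatic. Under 7.4.2, "Decisions regarding dose interruptions or modifications will be made by the investigator in consultation with the medical monitor", and "The medical monitor must be notified of dose interruptions due to AEs or laboratory abnormalities noted in Table 5". Entry also excludes AST or ALT above 2 × ULN.

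Much of this stands, and it is why the point is minor. A reader might infer that the protocol never orders an INR, or that dosing continues through the rise. Neither is so: Appendix 4 orders INR, and Table 5 holds drug above 3 × ULN.

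What does not stand is that these provisions close the gap. Investigator judgment, unscheduled tests and consultation permit an INR but do not require one. The Appendix 4 branch sits behind the 6.3.2.1 criteria. Footnote 2 can be read as making INR optional in general, but it more naturally exempts patients on anticoagulants. On either reading, 5.4.1 still contains the INR limb.

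**Conclusion.** The concern holds as a minor safety gap. Followed as written, the hold, retest and resume path lets a patient with an isolated, asymptomatic AST or ALT above 3 × ULN and bilirubin below 2 × ULN restart study medication with the INR limb of 5.4.1 untested. It is more than a missing detail, because a stated permanent-discontinuation rule cannot be applied on a path that the protocol itself lays down.

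The number affected is likely very small. That is a judgment resting on about 50 patients and the entry limit on AST/ALT, since no incidence is given. The conclusion also assumes that no document outside the protocol and SAP adds a reflex INR. The primary analysis, power and alpha are unaffected.

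A reader might infer that the whole liver stopping rule is unworkable; the documents do not support that, because the bilirubin, symptom, eosinophilia and >5 × ULN limbs can all be judged from data already ordered. A reader might also infer that every AST or ALT ≥3 × ULN should go straight to Appendix 4. That would add viral serology and a drug-level sample, and bring in a page that begins with immediate discontinuation and conflicts with Table 5, which allows resumption on enzyme values.

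**What to change.** In 7.4.2 and Table 5:

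- Whenever AST or ALT is above 3 × ULN, add a reflex INR to the first AST/ALT retest.
- Require INR ≤1.5 from that sample before study medication is resumed, except in patients on anticoagulants. A sample taken only at the point of restart could miss an INR that was raised earlier and has since recovered.

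An INR above 1.5 at that retest, with AST or ALT still above 3 × ULN, then leads to 5.4.1 and, through 6.3.2.1, to Appendix 4 as those sections already provide.

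The cost is protocol wording, one added assay and sample tube at a blood draw already required, and an occasional incidental INR result to follow up. No extra visit is needed. The SAP need not change: 12.6.2 already places all clinical laboratory results in the listings, and a reflex INR has no baseline or scheduled visit to summarise.

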6 DESCRIPTION OF STUDY ASSESSMENTS

Refer to Table 1 for the schedule of assessments.

6.1 Demographics and Other Screening Assessments

Safety assessments that are also part of the screening assessments are described in [Section 6.3](#).

6.1.1 *Medical History*

Medical history, including any ongoing illnesses, will be recorded in the eCRF, with the start date and stop date (if applicable) of the illness/condition. Medical history will be collected at the Screening Visit and updated, if necessary, on Day 1 prior to the first administration of study medication.

6.1.2 *Demographics*

Demographic data, including year of birth/age, sex, race, and ethnicity will be recorded in the eCRF.

6.1.3 *Tuberculosis Test*

An interferon gamma release assay/QuantiFERON Tuberculosis Gold Test for active/latent tuberculosis will be performed at the Screening Visit. The test will be provided by the central laboratory.

Patients who demonstrate evidence of latent tuberculosis infection (positive QuantiFERON Tuberculosis Gold Test) will only be allowed to participate in the study if there is documented evidence of a completed adequate treatment course for latent tuberculosis and if active tuberculosis is excluded per the investigator's judgment.

In case of indeterminate results, the test may be repeated once.

6.1.4 *SARS-CoV-2 Testing and Monitoring*

At Day 1, all patients entering the treatment phase of the study must have a nasopharyngeal (preferred) or oropharyngeal swab collected prior to the first dose of study medication to test for the presence of the SARS-CoV-2 virus. The sample will be sent to the study's central lab for analysis by reverse transcription polymerase chain reaction with results reported as either 'Detected' or 'Not detected' for SARS-CoV-2 viral particles. If central laboratory testing cannot be performed at the time of Day 1 (i.e., lab supplies are not yet available) and the study site is able to perform equivalent testing locally, they may choose to do so, as long as the test results are available in the patient's research chart for sponsor review. Patients should not initiate study medication

treatment in the absence of central laboratory or locally equivalent testing being performed.

Patients will be allowed to dose with study medication in the interval between sample collection at Day 1 and result reporting as long as there is no clinical suspicion of COVID-19 infection or recent significant exposure (close contact [<6 feet] for ≥ 15 minutes) of the patient to an individual with a confirmed, active infection.

If the patient's results are positive for SARS-CoV-2 following sample collection at Day 1, the patient will be notified immediately upon receipt of the results and treatment with study medication will be permanently discontinued. The patient will be advised to begin self-isolation and self-monitoring procedures according to any applicable local, state, and/or federal health recommendations. Referral to an appropriate health care provider for management of the patient's COVID-19 diagnosis should also be made. The patient should be seen for the PTFU Visit (see [Table 1](#)) only at such time that the investigator assesses the risk for incidental transmission from viral shedding to be minimized. The patient's COVID-19 diagnosis will be reported as medical history unless the patient's clinical course progresses such that criterion for SAE reporting is met (see [Section 8.3](#)), in which case, all applicable safety reporting procedures will be followed by the site.

Sites will also have the option to perform an unscheduled test for the SARS-CoV-2 virus at any time during the treatment phase of the study should a patient's clinical presentation necessitate it in the investigator's opinion. The same notification and referral procedures, as outlined in the preceding paragraphs, should be followed by the site. However, it is expected that any COVID-19 diagnosis made from a sample collected after the initiation of study be reported as an AE per the requirements of [Section 8](#) of this protocol.

